Subject units mean units within a group. For most research studies, a group will consist of individuals. However, the unit of interest in some research is not the individual. Examples:

- Dyads such as caregiver-and-Alzheimer's patient, or parent and child
- Families
- Other units, such as student-parent-teacher

Subject group means categories of subjects that are meaningful for the specific study. Some research has only one subject group – for example, all UW students taking Introductory Psychology. Some common ways in which subjects are grouped include:

- By intervention – for example, an intervention group, and a control group.
- By subject population or setting – for example, urban versus rural families
- By age – for example, children who are 6, 10, or 14 years old.

The IRB reviews the number of subjects in the context of risks and benefits. Unless otherwise specified if the IRB determines that the research involves no more than minimal risk: there are no restrictions on the total number of subjects that may be enrolled. If the research involves more than minimal risk: The number of enrolled subjects must be limited to the number described in this application. If it is necessary later to increase the number of subjects, submit a Modification. Exceeding the IRB-approved number ([over-enrollment](#)) will be considered non-compliance.

☐ **No** → Provide the rationale in the box below. Also, provide any other available information about the scope/size of the research. You do not need to complete the table.

Example: It may not be possible to predict the number of subjects who will complete an online survey advertised through Craigslist, but you can state that the survey will be posted for two weeks and the number who respond is the number who will be in the study.

Click or tap here to enter text.

☒ **Yes** → For each subject group, use the table below to provide the estimate of the maximum desired number of individuals (or other subject unit, such as families) who will complete the research.

Group name/description	Maximum desired number or individuals (or other subject unit) who will complete the research Provide numbers for the site(s) reviewed by the UW IRB and for the study-wide total number; example: 20/100
All patients who meet inclusion/exclusion criteria (single-arm study)	85

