We plan to extract data from the inpatient Electronic Medical Record (EMR), including demographic characteristics (age, gender, race, weight, height), diabetes history (diabetes type, home antidiabetic medications), vital signs, laboratory measurements (POC BG and laboratory venous BG, latest hemoglobin A1c, renal function), interventions (inpatient insulin dose and modality, glucocorticoid, pain medication, surgery or procedure), nutrition status (oral intake, tube feed, intravenous dextrose), and hospital admission/discharge dates.

Our UW observational cohort (STUDY00015475) has 1/140 patients (0.7%) who had hypoglycemia < 54 mg/dL during the first 24 hours of hospitalization. We think (and from prior inpatient glycemic trials) 3% increase (which means 3.7%) is considered clinically significant increase, so among these 85 subjects there cannot be more than $85 \times 3.7\% = 3.15$ subjects that develop hypoglycemia < 54 mg/dL. So, if we find more than 3.15 patients (round to 4) who develop BG < 54 during the recruitment, that is more than 3% increase. Because this is the first feasibility trial to apply the calculator on patients, we plan to enroll 10 subjects first, to demonstrate the calculator dose does not cause hypoglycemia (≤ 54 mg/dL). After these 10 participants are recruited, we will review and analyze these data. Then we will apply for a modification to increase the sample size.

To examine the feasibility, the specific outcomes that will be measured are hypoglycemia (< 54 mg/dL), mean BG during the first 24 hours of hospitalization, and hyperglycemia (≥ 300 mg/dL), compared to our UW observational cohort ([STUDY00015475](#)).

The International Hypoglycemia Study Group defined three levels of hypoglycemia for the purpose of standardized reporting: BG < 70 mg/dL (level 1), < 54 mg/dL (level 2), < 40 mg/dL (level 3) [1]. Centers for Medicare & Medicaid Services (CMS) use the same definition to capture hospital glycemic data [2]. BG < 54 mg/dL was defined as clinically significant hypoglycemia and used in prior inpatient glycemic trials [3].

For statistical analyses, trial subjects (single-arm study with utilization of the insulin calculator) will be compared with the UW observational cohort (STUDY00015475) where standard of care was used (mostly by physicians' experience). The primary endpoint is hypoglycemia < 54 mg/dL. The secondary endpoint is mean BG during the first 24 hours of hospitalization and hyperglycemia (≥ 300 mg/dL).

Reference

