Our UW observational cohort (STUDY00015475) has 1/140 patients (0.7%) who had hypoglycemia < 54 mg/dL during the first 24 hours of hospitalization. We think 3% increase (which means 3.7%) is considered clinically significant increase, so among these 85 subjects there cannot be more than $85 \times 3.7\% = 3.15$ subjects that develop hypoglycemia < 54 mg/dL. So, if we find more than 3.15 patients (round to 4) who develop BG < 54 during the recruitment, that is more than 3% increase. Because this is the first feasibility trial to apply the calculator on patients, we plan to enroll 10 subjects first, to demonstrate the calculator dose does not cause hypoglycemia (≤ 54 mg/dL). After these 10 participants are recruited, we will review and analyze these data. Then we will apply for a modification to increase the sample size.

UW inpatient insulin order set comes with hypoglycemia protocols which will be used to manage hypoglycemia if it occurs.

If hospitalists do not feel comfortable with the calculator doses when they enroll subjects, they will contact PI: [name] in real time, and we will double-check the calculator doses. If these subjects are admitted after midnight and PI: [name] is unavailable for discussion, hospitalists will not enroll the subject. Hospitalists and PI: [name] will then discuss this scenario (subject not enrolled) to understand the reasons hospitalists did not feel comfortable with the calculator dose.

10.2. [DETERMINATION] Reproductive risks. Are there any risks of the study procedures to subjects or partner of subjects related to pregnancy, fertility, lactation or effects on a fetus or neonate?

Examples: direct teratogenic effects; possible germline effects; effects on fertility; effects on a woman's ability to continue a pregnancy; effects on future pregnancies.

☒ **No** → Go to [question 10.3.](#)

☐ **Yes** → Answer the following questions:

10.2.a. Risks. Describe the magnitude, probability, duration and/or reversibility of the risks.

Click or tap here to enter text.

10.2.b. Steps to minimize risk. Describe the specific steps that will be taken to minimize the magnitude, probability or duration of these risks.

Examples: inform the subjects about the risks and how to minimize them; require a pregnancy test before and during the study; require subjects to use contraception; advise subjects about banking of sperm and ova.

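### Ten event-free subjects cannot demonstrate that the calculator dose is free of hypoglycemia: 0 of 10 excludes only rates above about 26%, against the plan's own limit of 3.7%

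*Combined protocol and SAP*

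**What the plan says.** Section 10.1 (Anticipated risks) sets a benchmark: "Our UW observational cohort (STUDY00015475) has 1/140 patients (0.7%) who had hypoglycemia < 54 mg/dL during the first 24 hours of hospitalization". It then sets the limit: "We think 3% increase (which means 3.7%) is considered clinically significant increase". The limit is turned into a count on the full sample, in a sentence that includes "so among these 85 subjects there cannot be more than" 3.15 affected subjects, followed by "So, if we find more than 3.15 patients (round to 4) who develop BG < 54 during the recruitment, that is more than 3% increase".

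The same paragraph introduces a first stage: "we plan to enroll 10 subjects first, to demonstrate the calculator dose does not cause hypoglycemia (≤ 54 mg/dL"). The data from these 10 are then to be reviewed and analyzed, and the next step is "Then we will apply for a modification to increase the sample size". Section 5.1 (Study procedures) repeats this text. Neither section gives a reason for choosing 10, a confidence level, or a statement of how an event in the first 10 would be read.

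Section 5.1 also states that "The primary endpoint is hypoglycemia < 54 mg/dL". Section 2.9 (Number of subjects) has a single row, "All patients who meet inclusion/exclusion criteria (single-arm study"), with a maximum of 85.

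**The concern.** Safety is the main purpose of this trial, and the first 10 subjects are the first patients dosed with the calculator. The plan says this stage will demonstrate an absence of harm. If that sentence is carried into the modification request, a clean result in 10 subjects could be presented as evidence of safety when it is compatible with rates far above the plan's limit.

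Two further points make the stage harder to interpret. First, its event definition differs from that of the primary endpoint, the cohort rate and the 4-event limit, so a reading of exactly 54 mg/dL counts in the first stage and nowhere else. Second, section 2.9 gives 85 while sections 5.1 and 10.1 describe an increase still to be applied for after 10. A reader cannot tell which number is currently in force.

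**Working it through.** **Inputs from the documents.** Cohort rate 1/140 and margin of 3 percentage points (section 10.1); full sample 85 (sections 2.9 and 10.1); first stage 10 (sections 5.1 and 10.1). The documents give no significance level for this stage, so both 95% conventions are shown.

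**1. The plan's own figure.** 1/140 = 0.714%, stated as 0.7%. Adding 3 points gives 3.7%. Then 85 × 0.037 = 3.145, which agrees with the stated 3.15. The count of 4 or more in 85 follows. No corresponding calculation is given for the 10-subject stage.

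**2. What 0 of 10 excludes.** With no events in n subjects, the exact (Clopper-Pearson) upper limit is 1 − α^(1/n).
- One-sided 95%: 1 − 0.05^(1/10) = 25.9%
- Two-sided 95%: 1 − 0.025^(1/10) = 30.8%

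Relative to the limit, 25.9/3.7 = 7.0 and 30.8/3.7 = 8.3.

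**3. How often a clean stage occurs anyway.** P(0 of 10) = (1 − p)^10.

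| True rate | P(no event in 10) | P(at least 1 in 10) |
|---|---|---|
| 0.7% (cohort, 1/140) | 93.1% | 6.9% |
| 3.7% (plan's limit) | 68.6% | 31.4% |
| 5% | 59.9% | 40.1% |
| 10% | 34.9% | 65.1% |
| 20% | 10.7% | 89.3% |

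A clean stage is only 93.1/68.6 = 1.36 times as likely at the cohort rate as at the limit, so it barely separates the two.

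**4. Subjects needed to exclude 3.7% with no events.** Solve (1 − 0.037)^n ≤ α.
- One-sided 95%: ln 0.05 / ln 0.963 = 79.5, so 80 subjects
- Two-sided 95%: ln 0.025 / ln 0.963 = 97.8, so 98 subjects

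**5. Event definition.** The first stage uses 54 mg/dL or lower. The endpoint, the cohort rate and the 4-event limit use below 54. The two definitions disagree only at exactly 54.

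**6. Numbers of subjects.** If 85 is approved now, no increase is needed to go past 10. If 10 is approved now, the 85 in section 2.9 is a planned total and is not labelled as one. If 85 reflects a modification already granted, the first-stage text is out of date. The documents do not say which of these holds.

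**The case against.** The strongest reply is that a lay sentence in an ethics application is being held to a criterion that was never set for it. The 3.7% limit and the 4-event count are computed on 85. The first 10 are introduced as a precaution because the calculator is new, and the plan neither defines success as 0 of 10 nor applies 3.7% at that point. A small lead-in is sensible in a feasibility trial. All of that stands, and it supports keeping the stage. It does not rescue the stated purpose, because demonstrating that the dose does not cause hypoglycemia is a claim about a rate, and 10 subjects cannot support it.

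Three stronger readings are tempting, and the documents do not support them.
- A reader might infer that enrolment would simply continue after 1 to 3 events in the first 10, since the only printed count is 4. Nothing says so. A review and a modification request come first, and the absence of a rule is not a rule to continue.
- A reader might infer that no first-stage rule exists. Section 10.6 says a Data and Safety Monitoring Plan was uploaded separately. It is not among these documents and may contain one.
- A reader might infer from the 85 in section 2.9 that the pause at 10 has no force. Sections 5.1 and 10.1 both commit to it. Section 2.9 asks for the maximum number desired to complete the research, so 85 can be read as the planned total. What remains is an inconsistency to reconcile.

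The cut-off difference is also fairly called minor. It affects one glucose value, errs in the stricter direction during the first stage, and looks like a drafting slip, although it appears in both sections.

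**Conclusion.** The claim made for the first stage is wrong as written. The best possible result, 0 of 10, excludes only rates above about 26% (one-sided 95%) or 31% (two-sided), roughly 7 to 8 times the plan's limit, and would occur 69% of the time if the true rate were exactly at that limit. The choice of confidence level does not change the conclusion. The calculation assumes independent subjects with a common event rate and takes the plan's 3.7% as given.

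The mismatch between 85 and the pending increase is a real inconsistency that needs one clear statement. The cut-off difference is a small correction. The point does not extend to the lead-in itself, which is reasonable, or to any finding that the trial lacks a first-stage rule or would run on past early events.

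**What to change.** - **Sections 5.1 and 10.1, purpose.** Replace the claim of demonstration with a procedure check and screen for gross harm. State that 0 of 10 excludes only rates above about 26% (one-sided 95%) and supports no safety conclusion against the 3.7% limit.
- **Sections 5.1 and 10.1, event.** Use the primary endpoint's definition at this stage, so that one definition runs through the first stage, the benchmark and the limit.
- **Section 2.9.** Reconcile the entry with the modification step by saying which number is approved now and which is the planned total. On the sequence described in 5.1 and 10.1, these would be 10 and 85. If 85 has already been approved, update the first-stage text instead.
- **Reading of early events.** State in 5.1 and 10.1 how one or more events in the first 10 will be read at the review. If the Data and Safety Monitoring Plan already covers this, cross-reference it.

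These are wording changes in three sections, with no added subjects or procedures. The downside is that the sponsor can say less after the first 10.

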2. PARTICIPANTS

2.1. [DETERMINATION] Participants. Describe the general characteristics of the subject populations or groups, including age range, gender, health status, and any other relevant characteristics.

Document Date & Version

06.29.2023

Version 4.6

APPLICATION IRB Protocol

Researcher Date & Version

mm/dd/yyyy

Version x.x

Page 7 of 55

We plan to recruit adult patients who are admitted to UW Montlake, Harborview and Northwest hospitals with history of type 2 diabetes mellitus on insulin therapy prior to admission. Because we work with the internal medicine hospitalist group, these patients are admitted for various non-critical acute illnesses from the emergency room. They can also be non-emergent admissions from the clinics. The obstetrics ward tends to use a different glycemic goal than other inpatient populations, so we exclude patients admitted to obstetrics ward. Our prior observation cohort did not include patients admitted for elective surgery or procedure, so our calculator has not been validated in this population.

2.2. [DETERMINATION] Inclusion and exclusion criteria.

2.2.a. Inclusion criteria. Describe the specific criteria that will be used to decide who will be included in the research from among interested or potential subjects. Define any technical terms in lay language.

1. Patients who are admitted to University of Washington Medical Center – Montlake, Harborview and Northwest hospitals
2. Aged ≥ 18 years
3. With history of type 2 or steroid-induced diabetes mellitus
4. Receiving insulin therapy prior to admission

2.2.b. Exclusion criteria. Describe the specific criteria that will be used to decide which of the subjects who meet the inclusion criteria listed above will be excluded from the research. Define any technical terms in lay language.

1. Patients who are admitted to ICU or obstetrics ward
2. Patients who are admitted for elective surgery or procedure
3. Patients who present with diabetic ketone acidosis, hyperosmolar hyperglycemic state or need IV insulin infusion
4. Patients who have no meal intake for 24 hours prior to admission, planned nothing per oral (NPO) during the first 24 hours after admission
5. Patients who report low appetite (25% or less) on admission or have a significantly decreased level of consciousness that study team does not think they are going to eat right after admission
6. Patients who receive enteral feeding after admission

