7. Patients who develop severe acute kidney injury needing dialysis therapy

2.3. [DETERMINATION] Prisoners. IRB approval is required in order to include prisoners in research, even when prisoners are not an intended target population.

Is the research likely to have subjects who become prisoners while participating in the study?

For example, a longitudinal study of youth with drug problems is likely to have subjects who will be prisoners at some point during the study.

☒ **No**

☐ **Yes** → If a subject becomes a prisoner while participating in the study, will any study procedures and/or data collection related to the subject be continued while the subject is a prisoner?

☐ **No**

☐ **Yes** → Describe the procedures and/or data collection that will continue with prisoner subjects.

Click or tap here to enter text.

2.4. [DETERMINATION] Will the proposed research recruit or obtain data from individuals that are known to be prisoners?

For records reviews: if the records do not indicate prisoner status and prisoners are not a target population, select “No”. Review the guidance on [Prisoners](#) for the definition of “prisoner”, which is not necessarily tied to the type of facility in which a person is residing.

☒ **No**

☐ **Yes** → Answer the following questions (**2.4.a. – 2.4.d.**)

2.4.a. Describe the type of prisoners, and their locations(s).

Click or tap here to enter text.

2.4.b. One concern about prisoner research is whether the effect of participation on prisoners’ general living conditions, medical care, quality of food, amenities, and/or opportunity for earnings in prison will be so great that it will make it difficult for prisoners to adequately consider the research risks. How will the chances of this be reduced?

Click or tap here to enter text.

2.4.c. Describe what will be done to make sure that (a) recruitment and subject selection procedures will be fair to all eligible prisoners and (b) prison authorities or other prisoners will not be able to arbitrarily prevent or require particular prisoners from participating.

Click or tap here to enter text.

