5. PROCEDURES

5.1. [DETERMINATION] Study procedures. Using lay language, provide a complete description of the study procedures, including the sequence, intervention, or manipulation (if any), drug dosing information (if any), blood volumes and frequency of draws (if any), use of records, time required, and setting/location. If it is available: Upload a study flow sheet or table to **Zipline**.

For studies comparing standards of care: It is important to accurately identify the research procedures. Review the section titled, "When to describe risks for studies evaluating medically recognized standards of care" in the [Identifying and Describing Reasonably Foreseeable Risks in Research](#) guidance and the draft guidance from the federal Office of Human Research Protections, "[Guidance on Disclosing Reasonably Foreseeable Risks in Research Evaluating Standards of Care](#)"; October 20, 2014.

Information about pediatric blood volume and frequency of draws that would qualify for expedited review can be found in this [reference table](#) on the Seattle Children's IRB website.

We plan to work with the internal medicine hospitalist group to conduct this study. There will be two lead hospitalists of contact at Montlake, Harborview and Northwest each. The screening hospitalists screen patients who need to be admitted to the hospital as their regular practice. In the meantime, they will screen eligible subjects who meet our inclusion/exclusion criteria.

Once eligible subjects are identified, screening hospitalists or admitting hospitalists will explain the rationales of this study and obtain informed consent. This process will be part of the standard admission interview which happens within one hour of admission. The interview happens either in the emergency room or hospital room, depending on whether a hospital room is immediately available.

This feasibility trial is designed as single-arm and mainly to investigate safety (no excessive hypoglycemia compared to standard of care). We will examine hyperglycemia as a secondary endpoint. We do not include a control arm in this study for comparison. The reason is it takes too many subjects to have enough power to detect potential excessive hypoglycemia (we plan a randomized study of a larger sample size after this feasibility trial to further exam the glycemic and clinical outcomes). For a feasibility trial, we would like to know if it is safe by testing on a small number of subjects.

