Our intervention will be only the initial insulin doses on admission. During the first few hours after hospitalization, subjects will have direct communications with their admitting hospitalists who are our research team. If subjects still have questions after talking to the admitting hospitalists, admitting hospitalists will contact PI: [name] to address subjects' questions as soon as possible during work hours. During the rest of the hospitalization and after hospital discharge, subjects will have PI: [name]'s office contact on the HIPPA form.

5.13. Future contact with subjects. Is there a plan to retain any contact information for subjects so that they can be contacted in the future?

☒ **No**

☐ **Yes** → Describe the purpose of the future contact, and whether use of the contact information will be limited to the study team; if not, describe who else could be provided with the contact information. Describe the criteria for approving requests for information.

Examples: inform subjects about other studies; ask subjects for additional information or medical record access that is not currently part of the study proposed in this application; obtain another sample.

Click or tap here to enter text.

5.14. Alternatives to participation. Are there any alternative procedures or treatments that might be advantageous to the subjects?

If there are no alternative procedures or treatments, select "No". Examples of advantageous alternatives: earning extra class credit in some time-equivalent way other than research participation; obtaining supportive care or a standard clinical treatment from a health care provider instead of participating in research with an experimental drug.

☐ **No**

☒ **Yes** → Describe the alternatives.

The currently available algorithms cannot precisely predict patients' initial insulin requirements. They are not supported by evidence either. Therefore, there is no standard alternative to participation. The current practice is hospitalists initiate insulin doses mostly by their own experience.

5.15. Upload to Zipline all data collection forms (if any) that will be directly used by or with the subjects, and any scripts/talking points that will be used to collect the data. Do not include data collection forms that will be used to abstract data from other sources (such as medical or academic records), or video recordings.

- **Examples:** survey, questionnaires, subject logs or diaries, focus group questions.

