If anytime the hospitalists decide subjects need to be on IV insulin infusion, they are no longer eligible for this study. In this case, they will be withdrawn from the research without their consent.

If hospitalists do not feel comfortable with the calculator doses and these subjects are admitted after midnight (PI: [name] is unavailable for discussion), hospitalists will withdrawal the subject from the research without their consent.

If the subject has already been given insulin before the study dosage can be administered, they will be withdrawn from the study

10.9. [DETERMINATION] Anticipated direct benefits to participants. If there are any direct research-related benefits that some or all individual participants are likely to experience from taking part in the research, describe them below:

Do not include benefits to society or others, and do not include subject payment (if any). Examples: medical benefits such as laboratory tests (if subjects receive the results); psychological resources made available to participants; training or education that is provided.

Participating in this study has the potential to achieve inpatient glycemic goal of 100-180 mg/dL faster than the standard of care with less manual adjustment.

10.10. [DETERMINATION] Return of individual research results.

Document Date & Version

06.29.2023

Version 4.6

APPLICATION IRB Protocol

Researcher Date & Version

mm/dd/yyyy

Version x.x

Page 50 of 55

In this section, provide your plans for the return of individual results. An “individual research result” is any information collected, generated or discovered in the course of a research study that is linked to the identity of a research participant. These may be results from screening procedures, results that are actively sought for purposes of the study, results that are discovered unintentionally, or after analysis of the collected data and/or results has been completed.

Review the guidance on [Return of Individual Results](#) for information about results that should and should not be returned, validity of results, the Clinical Laboratory Improvement Amendment (CLIA), consent requirements and communicating results.

10.10.a. Is it anticipated that the research will produce any individual research results that are clinically actionable?

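### The IV-insulin withdrawal rule can take already-dosed subjects out of the analysis, which would favour the calculator on the two secondary endpoints

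*Combined protocol and SAP*

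**What the plan says.** **Withdrawal (section 10.8).** "If anytime the hospitalists decide subjects need to be on IV insulin infusion, they are no longer eligible for this study". The next sentence adds: "In this case, they will be withdrawn from the research without their consent". The form's prompt asks whether withdrawal involves continued data collection; the answer does not say.

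**Entry criterion on the same subject (section 2.2.b, exclusion 3).** "Patients who present with diabetic ketone acidosis, hyperosmolar hyperglycemic state or need IV insulin infusion". This already covers patients who need IV insulin when they present.

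**Intervention (section 5.12).** "Our intervention will be only the initial insulin doses on admission". Section 5.1 leaves all later insulin adjustment to usual care and takes the outcome data from the EMR.

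**Exclusions 6 and 7 (section 2.2.b).** "Patients who receive enteral feeding after admission" and "Patients who develop severe acute kidney injury needing dialysis therapy". On consent and enrolment, section 5.1 says: "This process will be part of the standard admission interview which happens within one hour of admission".

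**Endpoints (section 5.1).** The primary endpoint is BG < 54 mg/dL. The secondary endpoints are mean BG in the first 24 hours and BG ≥ 300 mg/dL. All are compared with the 140-patient observational cohort.

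**Analysis set.** None is defined. The nearest text is the single row of the table in section 2.9: those meeting the entry criteria, 85 who complete.

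**The concern.** After the calculator dose has been given, no study treatment remains to stop. Withdrawing a subject at that stage can therefore affect only whether that subject's data are used. A need for IV insulin after a calculator-dosed regimen is closely tied to severe hyperglycemia, which the two secondary endpoints measure. Someone declared no longer eligible also falls outside the only description of the study group that the plan gives.

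If the data go, the trial group loses some of its worst glucose values while the external cohort may keep its own. The calculator would then look better on mean BG and on BG ≥ 300 for a reason unrelated to its performance. The decision to move to IV insulin is made by unblinded hospitalists who belong to the research team (sections 4.1 and 10.7), so a rule fixed in advance matters more. The results are meant to inform adjustment of the algorithm before a randomized trial (section 1.5).

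**Working it through.** **1. The plan's own figure.** Cohort rate 1/140 = 0.71%. Adding 3 percentage points gives 3.7%. 85 × 0.037 = 3.145 (3.157 with the unrounded rate), which matches the stated 3.15, so the limit is 4 subjects. The plan gives no alpha, power or dropout figure, so nothing else can be reproduced.

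**2. Which rules can act after the dose.**

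| Rule | Where | Can it act after the calculator dose? | Tied to an endpoint? |
|---|---|---|---|
| IV insulin needed | 10.8, withdrawal | Yes, no time limit | Yes: mean BG, BG ≥ 300 |
| Hospitalist uneasy with the dose after midnight | 10.8, withdrawal | No, decided before dosing | No |
| Insulin already given before the study dose | 10.8, withdrawal | No | No |
| Enteral feeding | 2.2.b, exclusion 6 | Unclear; worded as a later event | Not a glycemic outcome |
| Acute kidney injury needing dialysis | 2.2.b, exclusion 7 | Unclear; worded as a later event | Not a glycemic outcome |

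Only the first row clearly removes dosed subjects through an event related to an endpoint. Since mean BG covers only 24 hours, the rule could even remove a subject whose data for that endpoint are complete.

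**3. BG ≥ 300.** If x of 85 subjects have BG ≥ 300 and w of these are removed, the reported proportion is (x − w)/(85 − w). Neither x nor w is in the documents; both are assumed. Every removed subject is assumed to have had BG ≥ 300.

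| True | w = 1 | w = 3 | w = 5 |
|---|---|---|---|
| 8/85 = 9.4% | 7/84 = 8.3% | 5/82 = 6.1% | 3/80 = 3.8% |
| 17/85 = 20.0% | 16/84 = 19.0% | 14/82 = 17.1% | 12/80 = 15.0% |
| 26/85 = 30.6% | 25/84 = 29.8% | 23/82 = 28.0% | 21/80 = 26.3% |

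Replacing withdrawn subjects does not undo this if the rule also applies to the replacements.

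**4. Effect on the chi-squared test.** Simulation of 85 against 140, 40,000 runs, no true difference, two-sided 5% level (assumed), cohort not filtered for IV insulin (assumed). With a true rate of 20%, the chance of a significant result in the calculator's favour is 2.2% with no removals. It becomes 4.4%, 11.2% or 38.7% if 10%, 25% or 50% of the subjects with BG ≥ 300 are withdrawn. With 25% withdrawn it is 7.4% at a true rate of 10% and 13.8% at a true rate of 30%.

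**5. Mean BG.** If the removed subjects average g mg/dL above the full group, the mean moves by −w × g/(85 − w). With g = 120 (assumed):
- w = 2: −240/83 = −2.9 mg/dL
- w = 4: −480/81 = −5.9 mg/dL
- w = 6: −720/79 = −9.1 mg/dL

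**6. Primary endpoint.** The rule does not select on BG < 54. Losing an event-free subject leaves the count unchanged and raises the observed proportion; losing a subject with an event lowers the count. With three withdrawals and no replacement, 82 × 0.037 = 3.03, so the limit stays at 4. With five, 80 × 0.037 = 2.96, and 3/80 = 3.75% would exceed 3.7% without reaching 4. The probability of 4 or more events at a true rate of 6% (assumed) is 0.757 with all 85 kept. It is 0.723 if four subjects are lost for reasons unrelated to hypoglycemia and not replaced. It would fall to 0.535 if 25% of the events were lost, but nothing in the documents supports that share.

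**The case against.** **Data loss is inferred.** No passage says that a withdrawn subject's glucose values are discarded. The hypoglycemia limit counts patients who develop BG < 54 in the course of recruitment and is not restricted to completers. The data and safety monitoring plan was filed separately (section 10.6) and may cover this. This stands as a limit on certainty. It does not remove the problem, because 10.8 states a rule, was asked about continued data collection, and gave no answer.

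**The event may be rare.** ICU admissions and patients who need IV insulin at presentation are already excluded, so few dosed subjects may be affected. That stands, and the size is unknown.

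**The cohort may match.** If the 140 patients were filtered for IV insulin, the comparative bias shrinks. Section 1.8.b mentions only exclusion for low oral intake, so this is open.

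**Stronger readings the documents do not support.**
- A reader might infer that every glycemic endpoint is biased. For BG < 54 the rule does not select on the outcome, and neither direction nor size is established.
- A reader might infer that exclusions 6 and 7 remove dosed subjects by outcome. They are entry criteria, 10.8 does not list them as triggers, and neither is a glycemic outcome. The extracted data include "nutrition status (oral intake, tube feed, intravenous dextrose", which fits keeping tube-fed subjects. What remains is an ambiguity: later events are used as criteria when enrolment happens within an hour of admission.
- A reader might infer that a smaller denominator invalidates the limit of 4. At 82 subjects it does not, and because 85 is the number to complete, withdrawn subjects might be replaced.

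**Conclusion.** The point holds for the IV-insulin rule. Applied after the calculator dose and with the data dropped, it would bias mean BG in the first 24 hours and BG ≥ 300 in favour of the calculator, unless the cohort was filtered in the same way. For the primary endpoint the risk is only that an event could go uncounted. Exclusions 6 and 7 need clarifying but are not shown to remove anyone after dosing.

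The size cannot be obtained from the documents. The drop of about 3 percentage points (20.0% to 17.1%) rests on an assumed 20% rate and three withdrawals, all with BG ≥ 300. The test error rates further assume a 5% two-sided level and an unfiltered cohort.

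This should be fixed. It does not rank higher because the established bias concerns secondary endpoints of a feasibility trial whose main question is hypoglycemia.

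**What to change.** 1. Define the analysis set as every subject who received the calculator dose.
2. In 10.8, state that IV insulin, enteral feeding or dialysis starting after that dose does not remove the subject, or the subject's EMR glucose values through 24 hours of hospitalization, from the analysis.
3. State that exclusions 6 and 7 apply only to what is known at screening, and leave eligibility otherwise unchanged. In particular, the new wording should not bar all dialysis before the dose: exclusion 7 concerns acute kidney injury only, and broadening it would change who may enter.
4. Report the number of subjects with each of these events, and all withdrawals with reasons.
5. Apply the same rule to the 140-patient cohort and say how it was filtered.

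Optionally, add a sensitivity analysis that counts the start of IV insulin as a BG ≥ 300 event. It should not be the main analysis, because it may score values that were never observed.

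The cost is a few sentences in 2.2.b, 5.1 and 10.8, plus a check of the cohort data. The trial's glucose values are already in the EMR. Clinical care does not change, and the decision to start IV insulin is untouched. The downside is that the secondary results may look slightly less favourable.
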